3.7 Preliminary Safety in Humans

The first 6 cohorts of this study have been completed including subjects receiving a single 5 mg dose. No significant adverse effects were reported in any subjects receiving a single or multiple doses of the LSALT peptide.

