3.8 Study Rationale

Acute kidney injury is a devastating complication for patients undergoing surgery, diagnostic imaging or in the context of critical illness. Currently there are no effective therapies to prevent or minimize acute kidney injury. Inflammation is an important factor

¹ An allergic reaction is marked by the activation of the immune system by an allergen and includes signs that involve the skin, nose/throat, upper airway, GI tract, lungs and cardiovascular system. While the animals exhibited clinical features that would be seen in an allergic reaction, given its self-limited nature and severity, and the fact that they occurred only during the infusion, the findings are considered to represent a non-immune infusion reaction. Thus, the effects were considered pseudo-allergic or anaphylactoid.

in the pathogenesis of acute kidney injury. Given its favorable initial toxicology profile, the administration of LSALT peptide to target inflammation and prevent acute kidney injury has the potential to provide a significant clinical impact. Since LSALT peptide is a new drug, this phase I study to evaluate safety and pharmacokinetics is the first step needed to advance the LSALT peptide for the prevention of acute kidney injury in humans.

A third MAD cohort of 5 mg administered intravenously daily for 3 days is being proposed to obtain additional pharmacokinetic data.

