Study Day	Screen -29 to -2	-1	1	2	4	7
In patient period		X	X			
Informed consent	X					
Vital signs	X	X	X ⁴	X	X	X
Physical Exam	X	X		X	X	X
Alcohol Breath Test	X	X				
Drugs of Abuse ⁶	X	X				
Urinalysis	X	X		x		X
CBC	X	X		X		X
Chemistry	X	X		X		X
Creatine/eGFR	X	X		X		X
LFTs	X	X		X		X
PK			X ¹	X ²	X ³	X
INR/PTT	X			X		
CXR	X					X
ECG	X	X	X ⁵	X	X	X
B-hCG ⁷	X	X				X
Adverse Event	X	X	X	X	X	X
LSALT Administration			X			
Discharge from unit				X		
Follow up					X	X

Note: Fasting for blood sampling required for Screening and post dose Follow up. Participants will be required to have fasted from all food and drink except water for at least 8 hours prior to blood sampling.

1. PK blood samples: 5 ml of blood will be drawn at 30 mins pre (+/- 5 mins) and 15 mins (+/- 5 mins), 30 mins (+/- 5 mins), 45 mins (+/- 5 mins), 1h (+/- 5 mins), 2h (+/- 5 mins), 4h (+/- 10 mins), 6h (+/- 10 mins), 8h (+/- 10 mins), and 12h (+/- 30 mins) after the LSALT infusion has completed
2. PK blood sample: 24 hours (+/- 30 mins) after infusion has completed
3. PK blood sample: 72 hours (+/- 30 mins) after Infusion has completed

4. Vital signs dosing day (seated): pre dose within 30 mins prior to infusion start), 1 hour (+/- 10mins), 2 hour (+/- 10 mins) 6 hours (+/- 15min) and 10 hours post completion of infusion (+/- 30 mins)
5. 12 lead electrocardiogram (supine): pre dose (+/- 30 mins), 2 hours (+/- 15 mins) and 8 hours post completion of infusion (+/- 30 mins)
6. Repeat Drugs of Abuse (DoA) is permitted at the discretion of the Investigator
7. Pregnancy test will be via serum B-hCG at Screening and a urine pregnancy test at pre dose (Study Day -1/Day 12) and follow up

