7.2.5 MAD Study Procedures

- **Day -29. Pretreatment Evaluation and Randomization.** 29 days prior to study initiation, enrolled participants will undergo informed consent, followed by a complete history and physical examination (including body weight and height) vital signs (seated), alcohol breath test, drugs of abuse test, baseline fasting laboratory studies (CBC, clinical chemistry) including coagulation profile (INR and PTT), urinalysis, 12-lead, electrocardiogram (supine) and chest x-ray (single PA view). Women of child-bearing age will have a β -hCG to rule out pregnancy. Participants will then be randomized.
- **Day -1.** Admission to unit. Participants will undergo a clinical evaluation including complete vital signs and physical examination, 12-lead electrocardiogram (supine), drugs of abuse and alcohol breath test, urinalyses, 25 ml of blood drawn for safety laboratory investigations including CBC, clinical chemistries, urinalysis and women of child-bearing age will have a urine pregnancy test to rule out pregnancy.
- **Day 1.** Participants will undergo clinical evaluation including vital signs. 5 ml of blood will be drawn at 30 minutes prior to LSALT peptide infusion for baseline PK measurements. LSALT peptide infusion will begin and run over 2 hours. 5 ml of blood will be drawn at 15, 30, 45 60, 75, 90, 105, 120, 125, 130, 135, 140 minutes, and 3 hours from the onset of the LSALT infusion.

- **Day 2.** Participants will undergo a clinical evaluation, including vital signs, a brief history and symptom directed physical exam. 25 ml of blood will be drawn for laboratory investigations, including CBC, clinical chemistries and coagulation profile (INR and PTT), urinalysis and 24 hour PK sample (from the onset of the first LSALT infusion). An ECG will also be completed. If the participant shows no adverse events, they will receive the second dose of the LSALT peptide.
- **Day 3.** Participants will undergo a clinical evaluation, including vital signs, a brief history and a symptom directed physical exam. If the participant shows no adverse events, they will receive the third dose of the LSALT peptide. 5 ml of blood will be drawn at 15, 30, 45 60, 75, 90, 105, 120, 125, 130, 135, 140 minutes, and 3 hours from the onset of the LSALT infusion.

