- **Day 4.** Participants will undergo a clinical evaluation, including vital signs and a symptom directed physical examination. 25 ml of blood will be drawn for laboratory investigations, including CBC, clinical chemistries, coagulation profile (INR and PTT) and a 72 hour PK sample (from the onset of the first LSALT infusion). A urinalysis, CXR and ECG will also be completed. If the participant shows no adverse events, they will be discharged from the unit.
- **Day 7.** Participants will return for a clinical evaluation, including a brief history, vital signs and a symptom directed physical examination. 25 ml of blood will be drawn for laboratory investigations, including CBC, clinical chemistries, coagulation profile (INR and PTT) and a 96 hour PK sample (from the end of the 3rd LSALT infusion). A urinalysis will also be completed.
- **Day 14.** Participants will return for a clinical evaluation, including a brief history, vital signs and symptom directed physical examination. 25 ml of blood will be drawn for laboratory investigations, including CBC, clinical chemistries. A urinalysis will also be completed and a sample of blood drawn for anti-drug antibodies.
- **Day 21.** Participants will return for a clinical evaluation, including a brief history, vital signs and a complete physical examination. 25 ml of blood will be drawn for laboratory investigations, including CBC, clinical chemistries. A urinalysis and ECG will also be completed. Women of child-bearing age will also have a urine pregnancy test
- **Day 28.** Begin Cohort 2 or 3. Conducted as per Cohort 1 to day 21.

Treatment and Assessment Timetable (MAD)

Study Day	Screen -29 to -2	-1	1	2	3	4	7	14	21
In patient period		X	X	X	X				
Informed consent	X								
Vital signs	X	X	X ⁶	X ⁶	X ⁶	X	X	X	X
Physical Examination	X	X		X	X	X	X	X	X
Alcohol Breath Test	X	X							
Drugs of Abuse	X	X							
Urinalysis	X	X		X		X	X	X	X
CBC	X	X		X		X	X	X	X
Chemistry	X	X		X		X	X	X	X
Creatinine/eGFR	X	X		X		X	X	X	X
LFTs	X	X		X		X	X	X	X
PK			X ¹	X ²	X ³	X ⁴	X ⁵		
INR/PTT	X			X		X	X		
CXR	X					X			
ECG	X	X	X ⁷	X ⁷	X ⁷	X			X

B-hCG ⁸	X	X							X
Adverse Event	X		X	X	X	X	X	X	X
Anti-Drug Antibodies								X	
LSALT Administration			X	X	X				
Discharge from unit						X			
Follow up							X	X	X

Note: Fasting for blood sampling required for Screening and post dose Follow up. Participants will be required to have fasted from all food and drink except water for at least 8 hours prior to blood sampling.

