1. PK blood samples: 5 ml of blood will be drawn at 30 prior to LSALT peptide infusion for baseline PK measurements. LSALT peptide infusion will begin and run over 2 hours. 5 ml of blood will be drawn at 15, 30, 45 60, 75, 90, 105, 120, 125, 130, 135, 140 (+/- 2 min) minutes, 3 hours (+/- 5 min) from the onset of the LSALT infusion
2. PK blood sample: 24 hours (+/- 30 mins) from the onset of the 1st infusion.
3. PK blood samples: 5 ml of blood will be drawn at 30 prior to LSALT peptide infusion. LSALT peptide infusion will begin and run over 2 hours. 5 ml of blood will be drawn at 15, 30, 45 60, 75, 90, 105, 120, 125, 130, 135, 140 (+/- 2 min) minutes and 3 hours (+/- 5 min) from the onset of the LSALT infusion
4. PK blood sample: 72 hours (+/- 30 mins) from the onset of the first LSALT infusion
5. PK blood sample: 96 hours (+/- 30 mins) from the end of the third LSALT infusion
6. Vital signs dosing day (seated): pre dose (+/-30 mins), 1 hour (+/- 10mins) , 2 hour (+/- 10 mins) 6 hours (+/- 15min) and 10 hours post completion of infusion (+/- 30 mins)
7. 12 lead electrocardiogram (supine): pre dose (+/- 30 mins), 2 hours (+/- 15 mins) and 8 hours post completion of infusion (+/- 30 mins)
8. Pregnancy test will be via serum B-hCG at Screening and a urine pregnancy test at pre dose (Study Day -1,) and follow up

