8.1. PK Sampling Schedule

SAD:

PK blood samples: 5 ml of blood will be drawn at 30 minutes pre (+/- 5 minutes) and 15 minutes (+/- 5 minutes), 30 minutes (+/- 5 minutes), 45 minutes (+/- 5 minutes), 1h (+/- 5 minutes), 2h (+/- 5 minutes), 4h (+/- 10 minutes), 6h (+/- 10 minutes), 8h (+/- 10 minutes), and 12h (+/- 30 minutes) after the LSALT infusion has completed; followed by 24h and 72h samples.

MAD:

Day 1 PK blood samples: 5 ml of blood will be drawn at 30 minutes pre start of infusion (+/- 5 minutes) and 15 minutes (+/- 5 minutes), 30 minutes (+/- 5 minutes), 45 minutes (+/- 5 minutes), 1h (+/- 5 minutes), 2h (+/- 5 minutes), 4h (+/- 10 minutes), 6h (+/- 10 minutes), 8h (+/- 10 minutes), and 12h (+/- 30 minutes) after the LSALT infusion has completed; followed by 24h sample.

Day 3 PK blood samples: 5 ml of blood will be drawn at 15 minutes (+/- 5 minutes), 30 minutes (+/- 5 minutes), 45 minutes (+/- 5 minutes), 1h (+/- 5 minutes), 2h (+/- 5 minutes), 4h (+/- 10 minutes), 6h (+/- 10 minutes), 8h (+/- 10 minutes), and 12h (+/- 30 minutes) after the 3rd LSALT infusion has completed; followed by 72h and 92h samples.

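### SAP 8.1 and the MAD concentration listing use PK sampling times that conflict with protocol 7.2.5 and 7.3.6, and some planned MAD AUC outputs do not fit the samples

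*SAP*

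**What the plan says.** **SAP 8.1, MAD.** Day 1 has a pre-dose sample, nine samples from 15 min to 12 h after the infusion ends, and a 24 h sample. Day 3 has the same nine times and no pre-dose sample, ending "and 12h (+/- 30 minutes) after the 3rd LSALT infusion has completed; followed by 72h and 92h samples". Listing 16.2.8.2.5.3 also counts from the end of infusion. The nine times are those of the single-dose timetable in protocol 7.1.4, footnote 1, which ends "and 12h (+/- 30 mins) after the LSALT infusion has completed".

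**Protocol 7.2.5 and 7.3.6.** Sampling runs from the onset of infusion: 15, 30, 45, 60, 75, 90, 105, 120, 125, 130, 135 and 140 minutes, then "minutes and 3 hours (+/- 5 min) from the onset of the LSALT infusion". A 24 h and a 72 h sample are counted from the first onset. The Day 7 draw is "a 96 hour PK sample (from the end of the 3rd LSALT infusion" in 7.2.5, but 7.3.6 counts its 96 hours from the onset of the third dose. Footnote 3 of the MAD timetable adds a Day 3 pre-dose draw ("5 ml of blood will be drawn at 30 prior to LSALT peptide infusion. LSALT peptide infusion will begin"), which the Day 3 text omits: "they will receive the third dose of the LSALT peptide. 5 ml of blood will be drawn at 15, 30, 45 60, 75".

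**Protocol 15.0.** Two pre-dose draws, then 0.5, 1, 2, 4, 6, 8, 12 and 24 h after drug administration, on Day 1 and (MAD) Day 3.

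**SAP 8.2.** AUC0-12 and AUC0-24 are labelled Day 1, and AUC0-tau Day 3. RAUC is the Day 3 AUC0-12 or AUC0-24 divided by its Day 1 counterpart.

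**The concern.** The SAP schedule and the 7.2.5 schedule cannot both describe the same MAD subject. The SAP uses scheduled times: concentrations are summarised by nominal time (8.3), and any interim PK parameters are computed from scheduled times (section 11). A wrong schedule in the SAP therefore mislabels those outputs.

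The planned parameters also depend on which schedule was followed. If 7.2.5 was followed, nothing lies between 3 h and 24 h, so a 0 to 12 h area has no sample behind it after 3 h. If the SAP times were followed, nothing lies within the infusion or at its end, so the peak is missed. RAUC cannot be programmed as written on either schedule, because its Day 3 numerator is not among the Day 3 parameters. The two documents also leave tau open: protocol 5.0 and SAP 3.3 allow dosing once or twice daily, while protocol 7.2.2 says once daily.

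**Working it through.** **1. One clock.** Minutes from onset, 2-hour infusion:

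| Source | Post-dose times on a dosing day |
|---|---|
| SAP 8.1 (end-of-infusion times + 120) | 135, 150, 165, 180, 240, 360, 480, 600, 840 |
| Protocol 7.2.5 and 7.3.6 | 15, 30, 45, 60, 75, 90, 105, 120, 125, 130, 135, 140, 180 |

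The common times are 135 and 180. The SAP has no sample from 0 to 120 minutes; 7.2.5 has eight. The SAP has five samples after 3 h and up to 14 h; 7.2.5 has none until 24 h. If protocol 15.0 means after the end of infusion, all eight of its post-dose times appear in SAP 8.1 Day 1.

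**2. Late samples.** Hours from first onset, taking doses at 0, 24 and 48 h:

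- 96 h from the end of infusion 3 (7.2.5): 48 + 2 + 96 = 146.
- 96 h from the onset of dose 3 (7.3.6): 48 + 96 = 144.
- SAP 92 h: 48 + 2 + 92 = 142 from the end, or 48 + 92 = 140 from the onset. Like for like it is 4 h early, against a protocol window of ±0.5 h.
- Protocol 72 h from first onset: 72 − 48 = 24 h after the third onset. Read as the SAP sentence runs, after the third infusion, it is 48 + 2 + 72 = 122 h, on Day 6, when there is no visit.

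**3. Illustrative size.** Inputs: one compartment, 2-hour infusion, no noise. Half-lives are 0.66 and 1.17 h (rat range, protocol 3.5); 2, 4 and 6 h are assumed. The 24 h value is treated as below the quantification limit. With k = ln 2 / half-life, C(t) = 1 − exp(−kt) up to 2 h, then C(2)·exp(−k(t − 2)); the true AUC0-inf is 2.

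The peak is at 2 h. The 7.2.5 times catch it, and the first SAP sample comes 0.25 h later, so the Cmax ratio is exp(−0.25k). At 0.66 h, k = 1.0502 and the ratio is exp(−0.2626) = 0.769.

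On SAP times the linear rule draws one trapezoid from 0 to 2.25 h. At 0.66 h it is (2.25/2) × 0.6749 = 0.759, against a true area of 1.357: a ratio of 0.559. Adding the other trapezoids and Clast/λz gives:

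| Half-life (h) | 0.66 | 1.17 | 2 | 4 | 6 |
|---|---|---|---|---|---|
| Cmax, SAP ÷ 7.2.5 | 0.769 | 0.862 | 0.917 | 0.958 | 0.972 |
| AUC0-inf ÷ truth, SAP times | 0.728 | 0.868 | 0.939 | 0.975 | 0.984 |
| AUC0-inf ÷ truth, 7.2.5 times | 1.004 | 1.001 | 1.000 | 1.000 | 1.000 |
| Extrapolated share, 7.2.5 times | 14.6% | 32.4% | 51.0% | 71.1% | 79.5% |

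**4. The 24 h value on 7.2.5 times.** C24/Cmax = exp(−22k), about 1e-10 at 0.66 h and 2e-6 at 1.17 h. Such a value would be expected to be below the limit. SAP 8.3 sets it to missing, leaving AUC0-24 and AUC0-tau unsupported beyond 3 h. At 4 and 6 h the ratio is 0.022 and 0.079. If the 24 h value is then quantifiable, the single linear 3 to 24 h trapezoid makes AUC0-24 1.65 and 1.35 times the truth.

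**The case against.** The strongest defence is that the SAP schedule has a source. Its Day 1 times contain every post-dose time in protocol 15.0 on an end-of-infusion reading, so the authors may have followed one part of an inconsistent protocol. That stands as an explanation. It means the protocol must be settled first. It does not rescue 92 h, the 72 h origin or the missing Day 3 pre-dose sample.

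Several limits also stand:

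- The rat half-lives come from 100 to 450 mg/kg, against 16.7 to 83.3 µg/kg in a 60 kg participant at 1 to 5 mg. Protocol 3.5 puts at least 90% of the peptide in the cellular compartment of whole blood, so one compartment is a convenience.
- Actual collection times are listed and used in the individual plots, so mislabelling can be corrected.
- SAP section 12 reports no changes from the protocol, but its title concerns changes of analysis, so this is only supporting evidence.
- Once or twice daily may be a design option that protocol 7.2.2 later settled. Tau still needs to be stated.

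A reader might go further and infer that the first two MAD cohorts followed the SAP times and the third followed 7.2.5. Protocol 3.7 reports "The first 6 cohorts of this study have been completed including subjects receiving a single 5 mg dose", and 3.8 adds "A third MAD cohort of 5 mg administered intravenously daily for 3 days is being proposed to obtain additional pharmacokinetic data". The documents do not support this. Protocol 7.2.5 runs Cohorts 2 and 3 as Cohort 1, and SAP 8.1 gives one MAD schedule for all. The count of six is also ambiguous, because SAP 3.6 numbers three SAD and three MAD cohorts 1 to 6 and leaves the low-dose group unnumbered.

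**Conclusion.** The point holds as a contradiction between documents, and within the protocol, on when MAD samples are taken, with two direct consequences for SAP 8.2: AUC0-12 has no supporting sample on 7.2.5 times, and RAUC asks for Day 3 areas defined only for Day 1. These follow from the text and need no model.

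The size is illustrative. For one identical profile, SAP times give a Cmax 0.77 to 0.86 and a linear AUC0-inf 0.73 to 0.87 of those on 7.2.5 times at rat half-lives. At assumed half-lives of 4 to 6 h both ratios are 0.96 to 0.98. The human half-life is not given.

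No bias in dose proportionality is shown. It would require schedules that differ by dose, which the documents do not state. If source data or the addendum cited in SAP section 2 show such a split, Cmax and AUC would not be comparable across MAD doses, and the direction would depend on the parameter. With only the 5 mg cohort on 7.2.5 times, the slope for a proportional drug would move by +0.155 to +0.087 for Cmax over half-lives of 0.66 to 1.17 h. For AUC0-t, with an assumed quantification limit of 1% of Cmax, it would move by +0.10 at 0.66 h and −0.13 at 1.17 h.

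Primary safety endpoints are untouched. This should be fixed before the MAD PK outputs are produced.

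**What to change.** 1. Reconcile protocol 7.2.5 (text and footnotes), 7.3.6 and 15.0, together with the addendum cited in SAP section 2, on the MAD sampling times, the Day 3 pre-dose sample and the origin of the 96 h sample.
2. Replace the MAD schedule in SAP 8.1 and Listing 16.2.8.2.5.3 with the reconciled one, giving one origin per sample: 72 h from first onset, and 92 h corrected to 96 h with its origin settled. Change Day 7 to Day 3 in the MAD PK table and figure shells. Confirm that every MAD cohort used this schedule. If not, state it per cohort and footnote the Cmax, AUC and dose-proportionality outputs.
3. Reconcile the once-or-twice-daily wording (protocol 5.0, SAP 3.3) with once daily (protocol 7.2.2), and state tau from the outcome. Define RAUC as Day 3 AUC0-tau divided by the Day 1 AUC over the same interval.
4. If the 7.2.5 times apply, drop AUC0-12. Report AUC0-24 and AUC0-tau only when the 24 h value is quantifiable, flagging the single 3 to 24 h interval. Otherwise report AUC0-inf with %AUCexp. A log-down rule for the declining phase is optional.

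The cost is a protocol clarification, SAP and shell wording, and minor PK programming. Samples already drawn are unaffected. The drawback is that RAUC may be missing where the 24 h value is below the limit, and a per-cohort schedule would document non-comparability across doses without removing it.

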8.2. Derived PK Parameters

SAD:

The following plasma PK parameters will be derived for the SAD study portion.

Parameter	Definition	Method of Determination
AUC ₀₋₂₄	Area under the plasma concentration-time curve, from time 0 to 24 hours.	Linear trapezoidal method
AUC ₀₋₁₂	Area under the plasma concentration-time curve, from time 0 to 12 hours.	Linear trapezoidal method
AUC _{0-t}	Area under the plasma concentration-time curve, from time 0 to the last measurable concentration.	Linear trapezoidal method
AUC _{0-inf}	Area under the plasma concentration-time curve, from time 0 extrapolated to infinity.	AUC _{0-t} + C _{last} /λ _z , where C _{last} is the last measurable concentration.
%AUC _{exp}	Percentage of AUC _{0-inf} due to extrapolation from the time of last concentration to infinity.	(1 - AUC _{0-t} /AUC _{0-inf}) * 100

This document is confidential.

Parameter	Definition	Method of Determination
C_{max}	Maximum observed plasma concentration.	Observed directly from data
T_{max}	Time to reach C_{max} . If the maximum value occurs at more than 1 timepoint, T_{max} is defined as the first timepoint with this value.	Observed directly from data
$t_{1/2}$	Apparent first-order terminal elimination half-life.	$\ln(2)/\lambda_z$
λ_z	Apparent first-order terminal elimination rate constant.	Estimated by linear regression of the terminal elimination phase of the log-linear drug concentration-time curve
Cl/F	Apparent total body clearance.	Estimated as Dose/AUC _{0-inf}
V_z/F	Apparent volume of distribution.	Estimated as Dose/(\mathbf{\lambda}_z \times AUC_{0-inf})

MAD:

The following plasma PK parameters will be derived for the MAD study portion, for Day 1 and Day 3.

Parameter	Definition	Method of Determination
AUC_{0-24}	Area under the plasma concentration-time curve, from time 0 to 24 hours. (Day 1)	Linear trapezoidal method
AUC_{0-12}	Area under the plasma concentration-time curve, from time 0 to 12 hours. (Day 1)	Linear trapezoidal method
AUC_{0-tau}	Area under the curve over a dosing interval at steady state (Day 3 only)	Linear trapezoidal method
AUC_{0-t}	Area under the plasma concentration-time curve, from time 0 to the last measurable concentration.	Linear trapezoidal method
AUC_{0-inf}	Area under the plasma concentration-time curve, from time 0 extrapolated to infinity.	$AUC_{0-t} + C_{last}/\lambda_z$, where C_{last} is the last measurable concentration.
$\%AUC_{exp}$	Percentage of AUC_{0-inf} due to extrapolation from the time of last concentration to	$(1 - AUC_{0-t}/AUC_{0-inf}) * 100$

This document is confidential.

Parameter	Definition	Method of Determination
	infinity.	
C_{max}	Maximum observed plasma concentration on.	Observed directly from data
T_{max}	Time to reach C_{max} . If the maximum value occurs at more than 1 timepoint, T_{max} is defined as the first timepoint with this value.	Observed directly from data
$t_{1/2}$	Apparent first-order terminal elimination half-life.	$\ln(2)/\lambda_z$
λ_z	Apparent first-order terminal elimination rate constant.	Estimated by linear regression of the terminal elimination phase of the log-linear drug concentration-time curve.
Cl/F	Apparent total body clearance.	Estimated as Dose/ AUC_{0-inf}
V_z/F	Apparent volume of distribution.	Estimated as Dose/ $(\lambda_z \times AUC_{0-inf})$
RAUC	Accumulation Ratio for AUC.	$AUC_{0-12} \text{ or } AUC_{0-24} \text{ Day 3} / AUC_{0-12} \text{ or } AUC_{0-24} \text{ Day 1}$
RC_{max}	Accumulation Ratio for C_{max} .	$C_{max} \text{ Day 3} / C_{max} \text{ Day 1}$

Note: λ_z will be the negative of the estimated slope of the linear regression of the log-transformed concentration (natural logarithm) versus time profile in the terminal elimination phase. At least three concentration points will be used in estimating λ_z . The time point where log-linear λ_z calculation begins (λ_z Lower), and the actual sampling time of the last quantifiable concentration used to estimate the λ_z (λ_z Upper) will be reported with the correlation coefficient from the linear regression to calculate λ_z .

Note: tau is the dosing interval for steady-state data.

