15.0 PHARMACOKINETIC STUDIES

Blood samples will be drawn from participants for pharmacokinetic analysis at 15- and 30-minutes pre-dose and then 0.5, 1, 2, 4, 6, 8, 12 and 24 hours post drug administration on day 1 (SAD and MAD cohort) and day 3 (MAD cohort).

Pharmacokinetic analysis will be performed using validated analytic method.

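### On the protocol's MAD sampling grid, the SAP's linear trapezoidal rule draws one line from 3 h to 24 h and overstates AUC whenever the 24 h sample is measurable; the MAD schedules conflict and must be reconciled first.

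*SAP*

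**What the plan says.** SAP 8.2 gives the "Linear trapezoidal method" for every partial AUC and for AUC0-t, in both study parts, with no separate rule for falling concentrations. AUC0-inf adds the last measurable concentration divided by lambda_z. CL/F and Vz/F are computed from AUC0-inf. Lambda_z itself comes from a log-linear fit to the terminal phase.

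The documents contain three MAD sampling schedules.

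- **Protocol 7.2.5 (narrative and timetable footnotes) and 7.3.6.** On Days 1 and 3 the same-day samples end at "125, 130, 135, 140 minutes, and 3 hours from the onset of the LSALT infusion". The next sample after the first dose is "PK blood sample: 24 hours (+/- 30 mins) from the onset of the 1st infusion". After the third dose it is "PK blood sample: 72 hours (+/- 30 mins) from the onset of the first LSALT infusion".
- **SAP 8.1.** Day 1 samples run from 15 minutes to "6h (+/- 10 minutes), 8h (+/- 10 minutes), and 12h (+/- 30 minutes) after the LSALT infusion has completed; followed by 24h sample". Day 3 uses the same post-infusion times "after the 3rd LSALT infusion has completed; followed by 72h and 92h samples". The SAP's MAD concentration listing shell also times samples from the end of infusion.
- **Protocol 15.0.** Samples are taken before dosing, "then 0.5, 1, 2, 4, 6, 8, 12 and 24 hours post drug administration on day 1 (SAD and MAD cohort"), and likewise on Day 3 for MAD.

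SAP 8.3 sets values below quantification to missing once a measurable value has occurred. SAP section 12 reports no changes from the protocol's planned analysis.

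**The concern.** After an infusion ends, concentration falls roughly exponentially. A straight line between two points on a convex curve lies above it, and the excess grows with the fall between the points. The SAP treats the terminal decline as log-linear for lambda_z but as a straight line for area.

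On the Protocol 7.2.5 grid this affects the interval from 3 h to 24 h on both PK days. The inflated area passes into AUC0-24, AUC0-tau, AUC0-t and AUC0-inf, and through AUC0-inf into CL/F, Vz/F and the dose-proportionality model of SAP 8.4. The line exists only for participants whose 24 h value is measurable. If measurability depends on dose, the error does too.

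**Working it through.** The documents state no AUC or bias figure, so there is none to reproduce.

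**Inputs.** Infusion of 2 h and the sampling times above (Protocol 7.2.5). Dosing once daily (Protocol 7.2.2), so the 72 h sample falls 72 − 48 = 24 h after the third onset and the same 21 h gap applies on Day 3. Protocol 5.0 and SAP 3.3 allow once or twice daily; those passages need reconciling. Human half-life and assay limit are not given. The half-lives below are assumptions; only the rat values (0.66 to 1.17 h, Protocol 3.5) are documented.

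**Segment 3 to 24 h.** With r = C24/C3 = 2^(−21/half-life), linear/true = [(1 + r)/2] × ln(1/r)/(1 − r). At 4 h, r = 2^(−5.25) = 0.0263, and the ratio is 0.513 × 3.64/0.974 = 1.92.

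**Whole AUC0-24 on the Protocol 7.2.5 grid.** The area before 3 h is densely sampled, so the ratio is close to 1 + (share of AUC0-24 after 3 h) × (segment ratio − 1). At 4 h this is 1 + 0.71 × 0.92 = 1.65. Direct evaluation for a noise-free one-compartment first dose gives:

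| Half-life (h) | C24/C3 | Segment linear/true | Share after 3 h | AUC0-24 linear/true | Linear-up/log-down |
|---|---|---|---|---|---|
| 3 | 0.0078 | 2.46 | 0.63 | 1.93 | 1.00 |
| 4 | 0.026 | 1.92 | 0.71 | 1.65 | 1.00 |
| 6 | 0.088 | 1.45 | 0.78 | 1.35 | 1.00 |
| 8 | 0.162 | 1.26 | 0.82 | 1.21 | 1.00 |
| 12 | 0.297 | 1.12 | 0.85 | 1.10 | 1.00 |
| 24 | 0.545 | 1.03 | 0.88 | 1.03 | 1.00 |

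**Rat half-lives.** C24/C3 is 2.6e-10 at 0.66 h and 4.0e-6 at 1.17 h. The 24 h value would very probably be below quantification and set to missing. AUC0-t then stops at 3 h, where linear/true is 1.004 and 1.001.

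**Clearance.** AUC0-inf ratio = 1 + (AUC0-24 ratio − 1) × (1 − share of AUC0-inf beyond 24 h). Those shares are 0.005, 0.019 and 0.070 at 3, 4 and 6 h, giving ratios of 1.92, 1.63 and 1.33. CL/F is therefore 0.52, 0.61 and 0.75 of its true value.

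**Dose proportionality.** Suppose exposure is truly proportional, group sizes are equal at 1, 2.5 and 5 mg, and only 5 mg is measurable at 24 h. The centred ln(dose) values are −0.842, 0.074 and 0.768, with sum of squares 1.303. The slope becomes 1 + (0.768/1.303) × ln(AUC0-inf ratio) = 1 + 0.589 × ln(ratio): 1.39, 1.29 and 1.17 at 3, 4 and 6 h. The SAP 8.4 interval for a five-fold range is 1 ± ln 2/ln 5, that is 0.569 to 1.431. If 24 h is measurable at all doses, the ratio is common to all and the slope stays at 1.

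**Accumulation ratio.** With 24 h measurable on Days 1 and 3, estimated/true is 0.9995, 0.9988, 0.9979 and 0.9977 at 3, 4, 6 and 8 h.

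**Other grids.** AUC0-24 estimated/true, with the SAP 8.1 24 h sample taken as 24 h from onset and Protocol 15.0 hours read from onset:

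| Half-life (h) | SAP 8.1 linear | SAP 8.1 log-down | Protocol 15.0 linear |
|---|---|---|---|
| 3 | 0.983 | 0.952 | 1.060 |
| 4 | 0.996 | 0.966 | 1.055 |
| 6 | 1.001 | 0.979 | 1.040 |
| 8 | 1.000 | 0.984 | 1.028 |

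On the SAP 8.1 grid one triangle spans 0 to 2.25 h and loses area, so linear excess later happens to offset part of the loss.

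**Bi-exponential decline, Protocol 7.2.5 grid.** With a 1 h phase plus a 6 or 12 h phase of weight 0.001 to 0.05, linear/true is 2.2 to 2.7 and log-down/true is 1.20 to 1.51.

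**The case against.** The strongest objection is that the gap may not exist. SAP 8.1, directly above the AUC rule, lists MAD samples to 12 h after the infusion, and Protocol 15.0 also lists 4, 6, 8 and 12 h. This stands. A reader might infer that a 21 h line will certainly be drawn, but the documents do not settle that. It does not dispose of the point either: the protocol's narrative, timetable footnotes and laboratory section agree on the sparse grid, and the SAP declares no departure from the protocol.

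A second objection is that log-down is not always the better rule. This also stands: on the SAP 8.1 grid it is slightly worse than linear.

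Third, a reader might infer that accumulation and proportionality are distorted in general. They are not. With 24 h measurable on both days, the accumulation ratio is wrong by at most 0.3% at 3 to 8 h, and a bias common to all doses leaves the slope unchanged. Distortion requires measurability to differ by dose or by day, and no assay limit is given to judge that.

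Fourth, the large figures rest on assumed half-lives. At a 3 h half-life C24 is only 0.6% of the end-of-infusion level, so it might not be measurable. PK is a secondary endpoint and the proportionality assessment is exploratory. These points limit the weight of the finding; they do not reverse the direction of the error.

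**Conclusion.** The point holds conditionally. If the Protocol 7.2.5 and 7.3.6 grid was used and the 24 h sample is measurable, the linear rule overstates AUC0-24, AUC0-tau (with a 24 h interval), AUC0-t and AUC0-inf. Under a one-compartment decline, the AUC0-24 excess runs from 93% at a 3 h half-life to 3% at 24 h. If human elimination is as fast as in the rat, the line would very probably not be drawn and this error is close to nil.

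The effect on proportionality is material only if measurability at 24 h differs by dose. With 5 mg alone measurable, slopes of 1.39 and 1.29 at 3 and 4 h use up most of the upper margin before any sampling error. The accumulation ratio is little affected when both days are measurable.

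The documents do not support the stronger readings that the gap is established or that log-down is right for every schedule listed. The conflict between schedules comes first, and the choice of AUC rule follows from it.

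**What to change.** 1. Reconcile the MAD PK schedules in Protocol 7.2.5/7.3.6, Protocol 15.0 and SAP 8.1. State in both documents the one actually used, by cohort if cohorts differed, and record any departure in SAP section 12.
2. If samples cover the infusion (the Protocol 7.2.5/7.3.6 grid, or Protocol 15.0 if timed from onset), specify linear-up/log-down for the MAD AUCs in SAP 8.2.
3. On the Protocol 7.2.5/7.3.6 grid, flag every AUC that spans the unsampled 3 to 24 h interval, because log-down can still leave about 20 to 50% error if the decline is bi-exponential. State how AUC0-24 and AUC0-tau are handled when the 24 h value is below quantification.
4. If the post-infusion-only grid of SAP 8.1 was used, do not present log-down as the remedy. The unsampled infusion phase dominates the error there, and the AUCs should carry that caveat.

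The cost is a software setting, a few lines of SAP text and a check of the actual collection times. No new samples are needed.
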